4.1.2 PHASE 3 SEGMENT

- a. Able to provide informed consent and have signed Informed Consent Form (ICF) prior to screening procedures;
- b. Men and non-pregnant women 18 years of age or older;
- c. Per investigator judgment, healthy or stable with pre-existing medical conditions that do not require significant change in medication or have led to a hospitalization in the 3 months prior to enrollment or who, in the judgment of the investigator, are unlikely to require a significant change in therapy or hospitalization for worsening disease through Day 56;
- d. Able and willing to comply with all study procedures;
- e. Working or residing in an environment with high risk of exposure to SARS-CoV-2 for whom exposure may be relatively prolonged or for whom personal protective equipment (PPE) may be inconsistently used, especially in confined settings. Examples include:
 - 1. Retail/service workers/educators (restaurant waitresses/waiters and bar workers, street vendors, store cashiers, hairdressers and barbers, veterinary staff, daycare workers, airport screening staff, school teachers and college professors teaching in-person classes, college students attending in-person classes, office workers and volunteers who have multiple brief exposures to people regularly)

INO-4800	COVID19-311
Inovio Pharmaceuticals, Inc.	Clinical Protocol

- 2. Factory workers (when working in confined settings with large numbers of employees, meat-packing facilities)
- 3. Drivers providing bus, taxi or shared ride services (e.g., Uber, Lyft) and delivery services
- 4. User of public transportation (e.g., bus, train, subway) or public facilities (e.g. gyms) at least 3 times weekly
- 5. Nursing home staff or correctional facility staff
- 6. Retirement community residents or adult day program attendees who are regularly eating, socializing and/or exercising in common areas
- 7. Person 51 years or older living in a multigenerational (at least 3 generations) household
- 8. First responders (emergency medical technicians, police who are regularly assigned on patrol) Note: Firefighters typically use face shields and other protective gear but may be considered if they regularly assist with medical emergencies in the field
- 9. Health care workers with prolonged patient interaction (includes nurses and nursing assistants, medical assistants and technicians, respiratory therapists, physical therapists, social workers, dentists and dental hygienists)
- 10. Others, if in the opinion of the PI, the risk of COVID-19 exposure is comparable to the examples above.
- f. Must meet one of the following criteria with respect to reproductive capacity:
 - 1. Women who are post-menopausal as defined by reported spontaneous amenorrhea for ≥ 12 months;
 - 2. Surgically sterile or has a partner who is sterile (i.e., vasectomy in males or tubal ligation, absence of ovaries and/or uterus in females). In the case of vasectomy, subjects should wait six (6) months post-vasectomy prior to enrolling;
 - 3. Use of medically effective contraception with a failure rate of < 1% per year when used consistently and correctly from screening until last dose. Acceptable methods include:
 - i. hormonal contraception including implants, injections or oral;
 - **ii.** two barrier methods, e.g., condom and cervical cap (with spermicide) or diaphragm (with spermicide);
 - iii. intrauterine device or intrauterine system;
 - **iv.** abstinence when this is the subject's preferred and usual lifestyle. Note: Periodic abstinence (e.g., calendar, ovulation, symptothermal, or postovulation methods) and withdrawal are not acceptable methods of contraception.

4.2 **EXCLUSION CRITERIA**

4.2.1 PHASE 2 SEGMENT

- a. Acute febrile illness with temperature > 100.4°F (38.0°C) or acute onset of upper or lower respiratory tract symptoms (e.g., cough, shortness of breath, sore throat);
- b. Positive serologic or molecular (RT-PCR) test for SARS-CoV-2 at Screening;
- c. Pregnant or breastfeeding, or intending to become pregnant or intending to father children within the projected duration of the trial starting from the Screening visit until 3 months following the last dose;
- d. Positive serum pregnancy test during screening or positive urine pregnancy test immediately prior to dosing;
- e. Known history of uncontrolled HIV based on a CD4 count less than 200 cells/mm³ or a detectable viral load within the past 3 months;

INO-4800	COVID19-311
Inovio Pharmaceuticals, Inc.	Clinical Protocol

- f. Is currently participating or has participated in a study with an investigational product within 30 days preceding Day 0 (documented receipt of placebo in a previous trial would be permissible for trial eligibility);
- g. Previous receipt of an investigational vaccine for prevention or treatment of COVID-19, MERS or SARS (documented receipt of placebo in previous trial would be permissible for trial eligibility).
- h. Medical conditions as follows:
 - Respiratory diseases (e.g., asthma, chronic obstructive pulmonary disease) requiring significant changes in therapy or hospitalization for worsening disease during the 6 weeks prior to enrollment;
 - History of hypersensitivity or severe allergic reaction (e.g., anaphylaxis, generalized urticarial or angioedema)
 - Uncontrolled hypertension, defined as resting systolic blood pressure >160 mm Hg or a resting diastolic blood pressure >100 mm Hg prior to first dose;
 - Uncontrolled diabetes mellitus (Hemoglobin A1c > 8.0%);
 - Malignancy within the past 2 years, with the exception of superficial skin cancers that only required local excision and non-metastatic prostate cancer not requiring treatment;
 - Cardiovascular diseases (e.g., myocardial infarction, congestive heart failure, cardiomyopathy or clinically significant arrhythmias) requiring changes in therapy or hospitalization for worsening disease during the 6 weeks prior to enrollment;
 - History of seizures within the past 2 years with the use of no more than a single antiepileptic agent;
- i. Immunosuppression as a result of underlying illness or treatment including:
 - Primary immunodeficiencies (conditions including hypothyroidism, Hashimoto's thyroiditis and vitiligo are allowed);
 - Long term use (≥7 days) of oral or parenteral glucocorticoids at a dose of ≥20 mg/day of prednisone equivalent (use of inhaled, topical, nasal, otic, and ophthalmic corticosteroids are allowed) in the prior 6 months;
 - Current or anticipated use of disease modifying doses of systemic anti-rheumatic drugs (e.g., azathioprine, cyclophosphamide, cyclosporine, methotrexate) and biologic disease modifying drugs such as TNF-α inhibitors (e.g., infliximab, adalimumab or etanercept);
 - History of solid organ or bone marrow transplantation;
 - History of or current receipt of any other clinically significant immunosuppressive drugs
 - Diagnosis of an autoimmune disease that may jeopardize the safety of the subject or require therapy that would interfere with study assessments or endpoint evaluation, or otherwise impact the validity of the study results.
- j. Lack of acceptable sites for ID injection and EP considering the skin above the deltoid and anterolateral quadriceps muscles. The following are unacceptable sites:
 - Tattoos, keloids or hypertrophic scars located within 2 cm of intended administration site;
 - ICD or pacemaker (to prevent a life-threatening arrhythmia) that is located ipsilateral to the deltoid injection site (unless deemed acceptable by a cardiologist);
 - Any metal implants or implantable medical device within the electroporation site;
- k. Blood donation or transfusion within 1 month prior to Day 0;
- I. Prisoners or subjects who are compulsorily detained (involuntary incarceration);
- m. Reported alcohol or substance abuse/dependence or illicit drug use (excluding marijuana use) within the prior 2 years;

INO-4800	COVID19-311
Inovio Pharmaceuticals, Inc.	Clinical Protocol

n. Any illness or condition that in the opinion of the investigator may affect the safety of the subject or the evaluation of any study endpoint.

4.2.2 PHASE 3 SEGMENT

- Acute febrile illness with temperature ≥100.4°F (38.0°C) or acute onset of upper or lower respiratory tract symptoms (e.g., cough, shortness of breath, sore throat) on Day 0 prior to dosing;
- Positive serologic test for SARS-CoV-2 at Screening (after approximately 402 subjects positive for SARS-CoV-2 serologic test are randomized, this criterion will apply to all remaining subjects);
- c. Pregnant or breastfeeding, or intending to become pregnant or intending to father children starting from the Screening visit until the last dose;
- d. Positive urine pregnancy test during screening or immediately prior to dosing;
- e. Known history of uncontrolled HIV based on a CD4 count less than 200 cells/mm³ or a detectable viral load within 3 months prior to screening;
- f. Is currently participating or has participated in a study with an investigational product within 30 days prior to Day 0 (documented receipt of placebo in a previous trial would be permissible for trial eligibility);
- g. Previous or planned receipt of an investigational (including Emergency Use Authorization (EUA) or local equivalent authorization) or licensed vaccine for prevention or treatment of COVID-19, MERS or SARS (documented receipt of placebo in previous trial would be permissible for trial eligibility);
- h. Immunosuppression as a result of underlying illness or treatment including:
 - Primary immunodeficiencies (conditions including hypothyroidism, Hashimoto's thyroiditis and vitiligo are allowed);
 - Long term use (≥7 days) of oral or parenteral glucocorticoids at a dose of ≥20 mg/day of prednisone equivalent (use of inhaled, topical, nasal, otic, and ophthalmic corticosteroids are allowed) in the past 6 months;
 - Current or anticipated use of disease modifying doses of systemic anti-rheumatic drugs (e.g., azathioprine, cyclophosphamide, cyclosporine, methotrexate) and biologic disease modifying drugs such as TNF-α inhibitors (e.g., infliximab, adalimumab or etanercept) or others;
 - History of solid organ or bone marrow transplantation;
 - History of or current receipt of any other clinically significant immunosuppressive drugs
 - Diagnosis of an autoimmune disease that may jeopardize the safety of the subject or require therapy that would interfere with study assessments or endpoint evaluation, or otherwise impact the validity of the study results.
- i. Lack of acceptable sites for ID injection and EP considering the skin above the deltoid and anterolateral quadriceps muscles. The following are unacceptable sites:
 - Tattoos, keloids or hypertrophic scars located within 2 cm of intended administration site;
 - Implantable-Cardioverter-Defibrillator (ICD) or pacemaker (to prevent a lifethreatening arrhythmia) that is located ipsilateral to the deltoid injection site (unless deemed acceptable by a cardiologist);
 - Any metal implants or implantable medical device within the electroporation site;
- j. Blood donation or transfusion within 1 month prior to Day 0;
- k. People who work remotely or in a socially distanced setting with minimal risk of exposure to SARS-CoV-2;
- I. Prisoners or subjects who are compulsorily detained (involuntary incarceration);

INO-4800	COVID19-311
Inovio Pharmaceuticals, Inc.	Clinical Protocol

- m. Reported alcohol or substance abuse/dependence or illicit drug use (excluding marijuana use) within the prior 2 years;
- n. Any illness or condition that in the opinion of the investigator may affect the safety of the subject or the evaluation of any study endpoint.

4.3 **DISCONTINUATION/WITHDRAWAL OF CLINICAL TRIAL SUBJECTS**

Subjects may withdraw consent at any time for any reason or be dropped from the trial at the discretion of the Investigator should any untoward effect occur. In addition, the Investigator or the Sponsor has the right to discontinue a subject from the trial at any time.

The Investigator must notify the Sponsor immediately when a subject has been discontinued/withdrawn due to an Adverse Event (AE). If a subject withdraws from the trial or is discontinued from the trial prior to trial completion, all applicable activities scheduled for the final trial visit (i.e., Day 393) should be performed at the time of discontinuation/withdrawal if the subject agrees. Any related AEs, AESIs, and/or Serious Adverse Events (SAEs) present at the time of discontinuation/withdrawal should be followed in accordance with the safety requirements outlined in Section 7.9.

Unless a subject refuses to continue participation, all follow-up visits and procedures should be completed as indicated in the Schedule of Events (Table 3 and Table 4) following the second dose whether or not the subject has completed both doses.

If a subject decides to be vaccinated with a non-study prophylactic COVID-19 vaccine, either authorized under emergency use or licensed, during the trial, subjects should provide details of the non-study COVID-19 vaccine received to study staff and subjects should be requested to remain in the trial until the last visit. Additionally, subjects should also be advised that we do not have adequate information about the safety and effectiveness of another prophylactic COVID-19 vaccine when received following the receipt of INO-4800. As is already the case, if a subject is enrolled and receives a non-study prophylactic COVID-19 vaccine, either authorized under emergency use or licensed, while on study, the Investigator should enter the details as a concomitant medication. The subject should be followed (according to the Schedule of Events outlined in Table 3 of the Protocol).

Should a subject fail to attend the clinic for a required study visit, the site should attempt to contact the subject and reschedule the missed visit as soon as possible. In cases where the subject does not return for the rescheduled visit or cannot be reached to reschedule the missed visit, the site should make every effort to regain contact with the subject (3 telephone calls and if that fails, then a certified letter to the subject's last known mailing address) so that the subject's disposition can be considered as withdrawn from the study (i.e. lost to follow-up). If the contact with subject is re-established, site should contact medical monitor to discuss whether subject can continue study treatment or follow-up visits for the study. For all other subjects withdrawing from the study, an alternative reason for discontinuation should be recorded in the eCRF.

Reasons for discontinuation/withdrawal from the trial may include but are not limited to the following:

- Subject withdrawal of consent at any time;
- Any medical condition that the Investigator or Sponsor determines may jeopardize the subject's safety if he or she continues in the trial;
- Investigator, DSMB or Sponsor determines it is in the best interest of the subject;
- Subject non-compliance.

INO-4800	COVID19-311
Inovio Pharmaceuticals, Inc.	Clinical Protocol

Every effort should be made to obtain information on subjects who withdraw from the trial. The primary reason for withdrawal from the trial should be documented on the appropriate CRF. However, subjects will not be followed for any reason after consent has been withdrawn. Data and/or samples collected prior to withdrawal of consent will be analyzed.

Reasons for discontinuing subject dosing may include but are not limited to the following:

- Adverse Event (Adverse Reaction);
 - The Investigator or trial coordinator must notify the Sponsor immediately when a subject has been discontinued/withdrawn due to an Adverse Event (AE).
- Any medical condition that may jeopardize the subject's safety if he or she continues on trial;
- Pregnancy.

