Dose selection for evaluation of efficacy in the Phase 3 segment will be based on Week 6 immunogenicity data and Week 8 safety data from the Phase 2 segment. Group-level unblinded summaries and analyses of safety will be produced once the Week 8 phone call visit data are completed for all subjects in the Phase 2 segment. Group-level unblinded summaries and analyses of immunogenicity will be produced once the Week 6 visit data are completed for all subjects in the Phase 2 segment. Subject treatment assignments will be unblinded after Phase 2 subjects have reached the Week 30 visit.

Phase 3 Segment – Efficacy

In the Phase 3 segment, approximately 6714 seronegative and 402 seropositive subjects 18 years of age and older will be randomized at a 2:1 ratio to receive either active investigational product (INO-4800, 2.0mg) or placebo (placebo for INO-4800). Approximately half of seronegative subjects and approximately half of seropositive subjects will be 18-50 years of age, and the other half will be \geq 51 years of age as is operationally feasible. Also, approximately 711 subjects will be \geq 65 years of age, if operationally feasible.

Subjects will be randomized in a stratified manner according to (a) age category (18-50 years vs. ≥51 years) on Day 0, and (b) presence of or absence on Day 0 of any of the following underlying medical conditions that increase risk of severe COVID-19 disease, per CDC criteria [1], as listed below:

- Cancer
- Chronic kidney disease

INO-4800	COVID19-311
Inovio Pharmaceuticals, Inc.	Clinical Protocol

- Chronic lung diseases, including Chronic obstructive pulmonary disease (COPD), asthma (moderate-to-severe), interstitial lung disease, cystic fibrosis, pulmonary hypertension
- Neurologic conditions including stroke or cerebrovascular disease, that do not impact cognition
- Diabetes (type 1 or type 2)
- Hypertension
- Heart conditions, such as heart failure, coronary artery disease, or cardiomyopathies
- HIV infection (CD4 count >200 cells/mm3 or undetectable viral load)
- Liver disease
- Obesity (BMI ≥ 30 kg/m2)
- Sickle cell disease or thalassemia, or
- Smoking (current or former smoker).

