6.1.1.1 Medical History

A medical history will be obtained by the Investigator or qualified designee at the time of Screening. Medical history will include all active conditions, and any other past conditions, as well as surgical procedures, that are considered to be clinically significant by the Investigator and/or having occurred within 3 months prior to Screening. Subjects should be queried about any history of Hepatitis B, Hepatitis C and HIV.

In the Phase 3 segment, subjects with a self-reported history of Hepatitis B or C must provide documentation of liver enzymes that are not significantly elevated within the past 3 months. If such a report of liver enzyme testing is not available, this testing should be performed at Screening. Subjects with a history of Hepatitis C without cirrhosis who have completed treatment and have proof of an undetectable viral load at least 12 weeks following treatment may be enrolled and do not require liver enzymes within the past months.

Subjects with self-reported HIV must provide documentation of controlled HIV infection based on a CD4 count greater than 200 cells/mm³ or an undetectable viral load within the past 3 months. If a recent CD4 count and/or viral load is not available, this testing should be performed at Screening.

Illnesses first occurring or detected after the signing of the informed consent, or during the study and/or worsening of an existing illness in severity, frequency or nature after signing of the informed consent are to be documented as AEs on the Case Report Forms (CRF). Prior treatments, defined as administered up to 12 weeks prior to the time of informed consent and stopped prior to dosing on Day 0, should be recorded in the CRF as prior medications. Concomitant treatments, defined as continuing on Day 0 or new treatments taken at or after Day 0, should be recorded in the CRF as concomitant medications.

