Urine samples will be tested by dipstick for glucose, protein, and hematuria at Screening (Phase 2 segment only) and at visits specified in the Schedule of Events (Tables 3 and 4). If abnormal (presence of protein, hematuria, or glucose \geq 1+), a microscopic examination should be performed.

Serology:

HIV antibody or rapid test will be measured at Day 0 only.

Antibodies to SARS-CoV-2 will be measured at Screening and at visits specified in the Schedule of Events (Tables 3 and 4).

Pregnancy Testing:

Pregnancy testing will be performed on women of childbearing potential (WOCBP). All women will be assumed to be of childbearing potential unless they are:

- Women who are post-menopausal as defined by reported spontaneous amenorrhea for ≥ 12 months;
- Women who are surgically sterile or have a partner who is sterile (i.e., vasectomy in males or tubal ligation, absence of ovaries and/or uterus in females). In the case of a vasectomy, subjects should wait six (6) months post-vasectomy to be considered sterile.

Phase 2: For WOCBP, a serum pregnancy test will be obtained at Screening and a urine pregnancy test will be performed immediately prior to any dosing and at the subject's last visit.

Phase 3: For WOCBP, a urine pregnancy test will be obtained at Screening and will be performed immediately prior to any dosing.

A negative result for urine β -HCG (test must have a sensitivity of at least 25 mIU/mL) must be available prior to each administration of IP. If the β -HCG test is positive, indicating that the subject is pregnant prior to completing the specified dose regimen, then no further IP

INO-4800	COVID19-311
Inovio Pharmaceuticals, Inc.	Clinical Protocol

will be administered. Every attempt should be made to follow pregnant subjects for the remainder of the study and to determine the outcome of the pregnancy (see Section 7.12).

DIARY

Diaries will be implemented in the Phase 2 segment of the protocol and at selected sites (estimated to include 711 subjects) in the Phase 3 segment. Subjects will be provided a diary to record the following solicited local and systemic AEs:

- Oral temperature and time taken (each daily entry before 11:59 pm)
- Solicited systemic symptoms
- Solicited local injection site symptoms
- Concomitant medications

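### Phase 3 exclusion (e) and the Section 6.1.1.1 definition of controlled HIV are not logical complements, so a subject with discordant CD4 and viral load is classed both ways

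*Protocol*

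**What the plan says.** Three parts of the Protocol describe HIV status in terms of CD4 count and viral load.

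- **Exclusion.** Section 4.2.2, criterion (e), and the same item in the synopsis: "Known history of uncontrolled HIV based on a CD4 count less than 200 cells/mm³ or a detectable viral load within 3 months" before screening.
- **Documentation.** Section 6.1.1.1: "Subjects with self-reported HIV must provide documentation of controlled HIV infection", and control is judged "based on a CD4 count greater than 200 cells/mm³ or an undetectable viral load within the past 3 months". The paragraph continues: "If a recent CD4 count and/or viral load is not available, this testing should be performed at Screening". Unlike the hepatitis paragraph before it, the HIV paragraph is not limited to Phase 3.
- **Stratification list.** The synopsis and Section 3.0 list, among the conditions that count towards factor (b), "HIV infection (CD4 count >200 cells/mm3 or undetectable viral load". Section 8.7 treats this factor as two levels: any listed condition present, or none.

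Phase 2 exclusion (e) in Section 4.2.1 uses the same either-or construction as Phase 3. The wording is the same in the 1.0USA and 2.0USA texts. No passage says which definition governs when the two results disagree.

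**The concern.** The exclusion and the documentation rule are meant to be two sides of one concept: uncontrolled HIV keeps a subject out, and proof of control lets a subject proceed. Joining the two results with 'or' on both sides breaks that. One adverse result is enough to exclude, and one favourable result is enough to document control.

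Eligibility then depends on which passage a site works from and which result it holds. Section 6.0 allows no waivers, and Section 8.4 admits to the per-protocol population only subjects free of protocol violations. That population, among baseline seronegative subjects, carries the primary efficacy analysis. A discordant subject enrolled on the strength of one result is an eligibility violation if the other result later comes to light. If it never does, the subject stays in the primary set.

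**Working it through.** No sample size, power or alpha figure is involved. The check is a logical one.

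**Rules as written**

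- Excluded under (e): CD4 < 200, or viral load detectable.
- Controlled under 6.1.1.1, and described by the list: CD4 > 200, or viral load undetectable.

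The negation of 'A or B' is 'not A and not B'. Passing (e) on known results therefore needs CD4 of at least 200 and an undetectable load. Section 6.1.1.1 asks for only one favourable result.

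**Every combination**

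| CD4 | Viral load | Excluded by 4.2.2(e) | Controlled by 6.1.1.1 / on the list | Agree? |
|---|---|---|---|---|
| < 200 | detectable | yes | no | yes |
| < 200 | undetectable | yes | yes | **no** |
| = 200 | detectable | yes | no | yes |
| = 200 | undetectable | no | yes | yes |
| > 200 | detectable | yes | yes | **no** |
| > 200 | undetectable | no | yes | yes |

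Both discordant patterns conflict. Concordant results do not, and the boundary value of 200 leaves no gap.

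**Does the testing sentence close the overlap?** Its 'and/or' allows two readings.

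1. Whichever result is missing must be obtained. The site then holds both results, and two sections classify a discordant pair in opposite ways.
2. One recent result suffices. The second may not be obtained, and (e), which turns on a known history, cannot be fully checked.

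Neither reading makes the two sections agree.

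**Reach into the primary analysis.** Section 8.5.1 uses an exact binomial calculation on the split of cases between arms, with the follow-up ratio k. It has no stratification term. The only route into the primary result is membership of the per-protocol set. Eligibility is settled before randomisation, so no direction of bias between arms is implied.

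**The case against.** The strongest answer is that Section 6.1.1.1 does not confer eligibility. It is a medical-history paragraph that adds a documentation duty. Section 6.1.1 requires sites to check every inclusion and exclusion criterion, and waivers are ruled out. This stands: a subject known to have a detectable load, or a CD4 below 200, is ineligible whatever 6.1.1.1 says. A reader might infer that the protocol admits discordant subjects, or that sites will dose them. The documents do not support either. What remains is that the text telling sites what proof to collect calls the same subject controlled.

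Second, the testing sentence may lead sites to obtain the missing result. That is one ordinary reading, so it cannot be said that the second value will go unmeasured. Equally, the wording does not secure it.

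Third, a reader might take HIV to be a stratum of its own, or expect the list to distort the analysis. HIV is one of twelve items under a single present-or-absent factor. Being on the list makes nobody eligible, and the primary analysis does not use the factor.

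Fourth, a subject with CD4 below 200 and an undetectable load may also meet Phase 3 exclusion (h) on immunosuppression, and (n) leaves room for investigator judgement. This may reduce the practical effect for one of the two patterns. It does not address a CD4 above 200 with a detectable load.

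The Day 0 HIV test does not settle the matter: "HIV antibody or rapid test will be measured at Day 0 only", and such a test gives neither a CD4 count nor a viral load.

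**Conclusion.** The inconsistency is real and follows from the text alone. Both discordant combinations are excluded by (e) and called controlled by 6.1.1.1, and no passage reconciles them. The consequence is uneven application between sites and avoidable eligibility violations that affect the per-protocol set.

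The size cannot be computed: the documents give neither HIV prevalence nor the frequency of discordant results, and the country list is open. Purely as an illustration, assume that 1% to 5% of subjects have HIV and that 10% to 30% of those are discordant. The affected share is then 0.01 × 0.10 = 0.1% to 0.05 × 0.30 = 1.5%. That is about 7 to 101 of the 6714 planned seronegative subjects, or 7 to 107 of all 7116. Both inputs are assumptions, and the upper figure combines both upper extremes and counts every discordant subject. A reader might take it as an estimate of wrongly enrolled subjects, but the documents give no basis for that. The true number is probably small, and the finding does not depend on it.

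The conclusion applies to the 1.0USA and 2.0USA texts. A fragment marked version 7.0 is also present, but its eligibility sections are not shown, so whether that version keeps the wording cannot be checked. This is worth correcting, but it does not threaten the trial's primary conclusion.

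**What to change.** Reconcile Phase 3 criterion (e) (Section 4.2.2 and synopsis), the HIV paragraph of Section 6.1.1.1, the stratification list (Section 3.0 and synopsis), and Phase 2 criterion (e) (Section 4.2.1 and synopsis), so that all give the same answer for a subject whose CD4 and viral load disagree. The test is logical: the definition of controlled HIV must be the exact negation of the exclusion, so if one joins the two results with 'or', the other must join them with 'and'. Then reword the testing sentence in 6.1.1.1 so that the results it calls for are those the reconciled rule needs. Which clinical rule applies is for the sponsor's clinical team.

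The cost is a few words in the next amendment and a short note to sites. Section 6.1.1.1 already provides for testing at Screening, so any additional testing should be limited to subjects with self-reported HIV.
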